#### 3.1 Target Accrual

36 participants undergoing mechanical thrombectomy will be recruited.

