#### **6.3 Randomisation procedure**

Randomisation will occur on the day of mechanical thrombectomy after informed consent but before the procedure is due to start. Participants will be centrally allocated to either sham or active stimulation in a 1:1 ratio with block randomisation. No minimisation is required. The allocation sequence is generated and validated by the Statistician which will then be provided to the device manufacturer (Afferent) to program the simulators accordingly. The allocation sequence will be concealed to all trial investigators. The stimulators will be numbered sequentially starting at 1, and programmed according to the random allocation sequence provided. There will not be a possibility to identify the treatment group by any markings on the stimulator boxes.

To register a patient into the VANS trial, research staff at the site will log on to a secure data entry platform hosted by Queen Mary University of London and complete the patient's details to obtain a unique patient identification number. The patients will be allocated to a sequential trial group ID corresponding to the stimulator box, starting with 1, then 2 and so on. All details of the eligibility screening process including participants who are screened and not randomised will be documented in the medical records.

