#### 10.12 Management of device-specific adverse events

Any device-specific adverse events (AEs) will be recorded in the patient medical records and eCRF and the information – in pseudo anonymised format – will be passed on to the delegated representative from Afferent Medical Solutions Ltd.

All AEs will be informed to the device manufacturer (Afferent Medical Solution Ltd) as soon as possible after the investigation site staff has become aware of the event. Details of the device-specific adverse will events be sent to the Afferent team on the following email [contact], and where possible, a member of the trial team will contact the Afferent team via phone at [name].

We anticipate following side effects associated with TAN applied via electrical stimulation for the tragus:

- Light-headedness
- Fatigue/tiredness
- Mood changes
- Neck pain
- Tooth pain
- Pain/local skin irritation due to attachment of the device ear clips
- Tingling sensation due to the use of the device
- Palpitations

AEs will be recorded in the medical notes and on the appropriate AE pages of the CRF corresponding to the visit or interaction with the study team. Serious adverse events (SAEs) require expedited reporting to the device manufacturer (Afferent Medical Solution Ltd) and the Sponsor or designee regardless of relationship to study device or study procedure (refer for more information to

Investigators Brochure 9.3). All those will be informed as soon as possible and within 24 hours of the Investigator/ Investigation site staff become aware of the event. Potential interactions with other therapies any Device related SAEs are not anticipated. However, if they occur, the Principal Investigator and Investigation site will follow Afferents SOPs for reporting and managing them. Please see CIP section 13 for further information.

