Adverse events and serious adverse events will be presented as a number (%) by treatment allocation. All patients with a recorded outcome will be included in the summary. In addition to this, 'other' adverse events will be reported separately if prevalence is more than 5% across all participants in the trial.

Protocol deviations

Numbers and percentages of protocol deviations will be reported. The following protocol deviations will be reported: (a) Patient who did not receive either or both leads; (b) other deviation. We will report the number of patients in each treatment group with at least one of the above protocol deviations. In addition to this, 'other' protocol deviations will be reported separately of prevalence is more than 5% in the trial.

References

- 1. Mistry, E.A., et al., *Blood Pressure Variability and Neurologic Outcome After Endovascular Thrombectomy: A Secondary Analysis of the BEST Study.* Stroke, 2020. **51**(2): p. 511-518.
- 2. White, I.R., et al., *Strategy for intention to treat analysis in randomised trials with missing outcome data*. BMJ, 2011. **342**: p. d40.
- 3. Montori, V.M. and G.H. Guyatt, *Intention-to-treat principle*. CMAJ: Canadian Medical Association journal = journal de l'Association medicale canadienne, 2001. **165**(10): p. 1339-1341.
- 4. White, I.R. and S.G. Thompson, *Adjusting for partially missing baseline measurements in randomized trials.* Statistics in Medicine, 2005. **24**(7): p. 993-1007.
- 5. Groenwold, R.H.H., et al., *Missing covariate data in clinical research: when and when not to use the missing-indicator method for analysis.* CMAJ: Canadian Medical Association journal = journal de l'Association medicale canadienne, 2012. **184**(11): p. 1265-1269.
- 6. Schulz, K.F., et al., *CONSORT 2010 Statement: updated guidelines for reporting parallel group randomised trials.* BMC Medicine, 2010. **8**(1): p. 18.
- 7. Yelland, L.N., et al., *Applying the intention-to-treat principle in practice: Guidance on handling randomisation errors.* Clinical Trials, 2015. **12**(4): p. 418-423.
- 8. Chalos, V., et al., *National Institutes of Health Stroke Scale: An Alternative Primary Outcome Measure for Trials of Acute Treatment for Ischemic Stroke*. Stroke, 2020. **51**(1): p. 282-290.

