HF, power				
HF, peak				
DFA1				
DFA2				

Table 6. Process/ exploratory measures.

	ACTIVE	SHAM
NIH Stroke Scale (NIHSS) 24h after mechanical thrombectomy (delta change from admission)		
Health status 7 days after mechanical thrombectomy.		
Alive		
Troponin change from admission (delta change from admission)		

Table 7:Adverse events

Adverse Events - no. (%)	active	sham
Patients with ≥ 1 adverse event		
Total number of adverse events		
Type of adverse event		
Cardiac arrythmia		
Local skin irritation		
Other

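### With 36 patients, the SAP's 5% pooled threshold leaves any adverse event type seen in only one patient unnamed in the planned adverse event output, apart from cardiac arrhythmia and local skin irritation

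*SAP*

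**What the plan says.** The SAP (section 5, Safety analyses) makes two commitments. The first carries no threshold: "Adverse events and serious adverse events will be presented as a number (%) by treatment allocation". The second is additional and concerns other events only: these "adverse events will be reported separately if prevalence is more than 5% across all participants in the trial". On the denominator, the SAP says "All patients with a recorded outcome will be included in the summary".

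Dummy Table 7 in SAP Appendix 3 has active and sham columns. Its rows are patients with at least one event, total events, and three types: cardiac arrhythmia, "Local skin irritation" and Other. It has no row for serious adverse events, and the SAP specifies no listing by event term.

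Protocol 10.12 introduces its own list with "We anticipate following side effects associated with TAN applied via electrical stimulation for the tragus". The list includes light-headedness, fatigue, mood changes, neck pain, tooth pain and tingling, none of which has a row in Table 7.

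On size, Protocol 3.1 says "36 participants undergoing mechanical thrombectomy will be recruited", and Protocol 6.3 says "Participants will be centrally allocated to either sham or active stimulation in a 1:1 ratio with block randomisation".

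**The concern.** A 5% cut-off for naming events keeps tables readable in a large trial. In a trial of 36 it separates one affected patient from two, so its only effect is to remove the names of event types seen once. The trigger is also pooled over both arms. One active patient is 5.6% of an arm of 18, but the rule looks at 2.8% of the trial.

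The protocol calls the study a pilot that collects data for a larger trial (13.1). The device is not approved for this use (10.0), and participants are frequently unable to consent for themselves (4.0). In that setting, the identity of a single unexpected event is part of what the next trial's safety monitoring would draw on. A reader of the planned table would see a count of one under Other and could not tell what it was, or whether it was serious or attributed to the device.

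**Working it through.** **Inputs.** Planned total 36 (Protocol 3.1 and 13.1; SAP, Sample size calculation). Allocation 1:1 (Protocol 6.3) in blocks of 4 (SAP, Randomisation procedure); 36 / 4 = 9 full blocks, so 18 per arm. Dropout allowance of 5 (Protocol 13.1), leaving 31. Threshold strictly above 5% of all participants (SAP section 5). The check assumes that the threshold applies to each event type, counted in patients.

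**The plan's own figure.** The SAP gives a coefficient of variation of 15 against 10, SD 4, 90% power, 5% level, and 5% non-compliance in each group. If non-compliance dilutes the difference to 5 × 0.90 = 4.5, a two-sided two-sample t-test needs 18 per arm, 36 in total. The denominator of 36 is reproduced.

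**What the threshold means in patients.**

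| Patients in denominator | One patient | Two patients |
|---|---|---|
| 36 | 1/36 = 2.78%, not named | 2/36 = 5.56%, named |
| 31 | 1/31 = 3.23%, not named | 2/31 = 6.45%, named |

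One patient exceeds 5% only when n is 19 or fewer (1/20 is exactly 5%). Dropout on the scale the protocol allows for does not change the result: the rule drops exactly the unlisted types seen in one patient.

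**How often that would matter.** The documents give no event rates, so 2%, 5% and 10% are assumptions. For n patients at risk p:

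- P(at least one) = 1 − (1 − p)^n
- P(exactly one) = n p (1 − p)^(n−1)
- Share of trials with the event that do not name it = P(exactly one) / P(at least one)

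For p = 5% in 18 active patients and none in sham: P(at least one) = 1 − 0.95^18 = 0.603; P(exactly one) = 18 × 0.05 × 0.95^17 = 0.376; share = 0.376 / 0.603 = 62%.

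For p = 5% in all 36: P(at least one) = 0.842; P(exactly one) = 0.299; share = 0.299 / 0.842 = 36%.

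| Assumed risk | Active arm only (n = 18) | Both arms (n = 36) |
|---|---|---|
| 2% | 0.255 / 0.305 = 84% | 0.355 / 0.517 = 69% |
| 5% | 0.376 / 0.603 = 62% | 0.299 / 0.842 = 36% |
| 10% | 0.300 / 0.850 = 35% | 0.090 / 0.977 = 9% |

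**Which events reach the table at all.** Protocol 10.12 sends device-specific adverse events to the eCRF and adverse events to the CRF's adverse event pages. Protocol 11.3 first asks for all adverse events to be documented in the notes and the CRF, then says that those not classed as serious will not be entered on the CRF as adverse events. These statements cannot all hold. If the last one governs, single unlisted events in the dataset would be serious ones, and the mild effects anticipated in 10.12 would be absent whatever the SAP threshold.

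**The case against.** The best defence is that this rule shapes one summary table and hides little.

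- **Events named elsewhere.** A reader might infer that no event type seen in one patient is ever named. The documents do not support that. Arrhythmia and local skin irritation have Table 7 rows at any count; Table 2 also shows arrhythmias and systolic pressure below 90 mmHg; 7-day status is reported; and infections within 7 days are quantified.
- **Arm.** A reader might infer that the arm of a single event is lost. Only the trigger is pooled. The Other row has a cell for each arm, so the event is counted where it occurred and only its label is missing.
- **Serious events.** A reader might infer that the SAP suppresses serious events. It promises serious event counts by arm without a threshold, and the 5% sentence does not mention them. What stands is narrower: Table 7 has no row for that promise, and nothing says serious or device-related events are named regardless of count.
- **Safety oversight.** A reader might infer that the trial loses the signal. Subject to stated exceptions, serious events are recorded individually and reported to the sponsor and manufacturer within 24 hours (Protocol 11.6), the Chief Investigator reviews them within 72 hours (11.7), and the IDMC sees unblinded data (23.3). None of these is a planned analysis output, so the gap in the reported results remains.
- **Size.** The percentages rest on assumed rates and are shares of trials, not of events. At 5% in the active arm only, 18 × 0.05 = 0.9 patients are expected to be affected, so the share of affected patients whose event goes unnamed is 0.376 / 0.9 = 42%, not 62%.

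The SAP has a parallel rule that other "protocol deviations will be reported separately of prevalence is more than 5% in the trial". A reader might extend the point to it. The safety argument above does not carry over to deviations, and no change to that rule is argued here.

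**Conclusion.** The point holds in a limited form. As written, the SAP names an unlisted adverse event type only when at least two of the 36 patients have it, or at least two of 31 after the allowed dropout. A type seen once is counted by arm under Other and not identified in the planned adverse event output, with no stated exemption for serious or device-related events. This is arithmetic on the documents' own figures and rests only on reading the threshold as applying to each event type.

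How often it would matter depends on rates that the documents do not give. At an assumed 5% risk, between about 36% (both arms) and about 62% (active arm only) of the trials in which the event occurs would not name it. Over assumed risks from 2% to 10% the range is 84% down to 9%.

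The change should be made. It concerns safety reporting only and does not affect the primary analysis, sample size or power.

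**What to change.** In the SAP:

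1. Delete the 5% threshold for adverse events in section 5.
2. Report every recorded event type by arm, both as number of patients and as number of events.
3. Add to Table 7 the serious adverse event row that the text already promises.
4. List every serious or device-related event by term and arm, whatever the count.

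In the protocol, reconcile 10.12 and 11.3 on whether non-serious events are entered on the CRF. Without that, removing the threshold may not bring the anticipated mild effects into the report.

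The SAP change costs a few sentences and a slightly longer table. Serious events are already to be recorded individually under Protocol 11.6, subject to its exceptions, so listing them should need little new data. If the reconciliation settles on recording non-serious events, there is some added data entry.

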Appendix 1: Derived outcomes and variables

Primary outcome

CV systolic blood pressure:
$$CV = \left(\frac{SD}{BP_{mean}}\right) * 100$$

Secondary outcomes

For both systolic BP (SBP) and diastolic BP (DBP), the following indices of blood pressure variability will be calculated:

1. Standard deviation SBP/DBP in the first 24h after mechanical thrombectomy.

$$SD = \sqrt{\frac{1}{(n-1)}\sum_{(i=1)}^{(n)} (BP_i - BP_{mean})^2}$$

2. Average real variability in the first 24h after mechanical thrombectomy.

$$ARV = \frac{1}{\sum_{k}^{w_k} \sum_{k=2}^{n} w_k \times |BP_k - BP_{k-1}|}$$

3. Successive variation in the first 24h after mechanical thrombectomy.

$$SV = \sqrt{(1/(n-1))\sum_{(i=1)}^{(n-1)} (BP_{i+1} - BP_i)^2)}$$

4. Residual standard deviation in the first 24h after mechanical thrombectomy.

$$rSD = \sqrt{\frac{\sum (BP - BPest)^2}{n - 2}}$$

Heart rate variability, time domain measures

RR-interval, SDNN, RMSSD, SD HR, NN, pNN

Frequency domain measures

VLF power, VLF peak, LF power, LF peak, HF power, HF peak, DFA1, DFA2.

Peak level of Troponin-T measured within 24 hours of MT

This is defined as the highest troponin-t value measured within 24 hours of mtwhich is collected on admission and 24h post MT [if applicable]. If only one troponin-T value is available, then this will be used as the peak. If troponin-T data is missing for both timepoints, then the outcome will be set to missing.

Infection up to 7 days after mechanical thrombectomy

This is defined as one or more of the following infections (definitions of each type of infection are the same used in the SPACE protocol):

- Superficial surgical site infection
- Deep surgical site infection
- Organ space surgical site infection
- Urinary tract infection
- Infection, source uncertain
- Laboratory confirmed blood stream infection

Equal to 1 if:

- At least one of the components of infection is listed as occurring Equal to 0 if:
- All of the components of postoperative infection are "None"

Missing if:

- All components are missing
- OR one or more of the components of postoperative infection is missing and all other components are "None"

Death and location 7 days after mechanical thrombectomy

Equal to 1 if:

• Patient status at 7-day follow-up is dead/in hospital

[figure not shown]
Equal to 0 if:

• Patient status at 7-day follow-up is alive / out of hospital

Missing if:

- Patient status at 30-day follow-up is missing
- Patient status at 30-day follow-up is marked as 'dead' and missing date of death

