#### Day seven follow-up

- Mortality status and in hospital stay seven days after mechanical thrombectomy
- Safety review

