	 Exclusion criteria participation in a trial exploring similar biological mechanism; previous enrolment; anatomical contraindication (local ear abnormalities); pregnancy.
Interventions	Active stimulation bilateral active transauricular nerve stimulation for the duration of the mechanical thrombectomy procedure (AffeX-CT/001 investigational device). The intervention will be repeated for 1h the morning following the mechanical thrombectomy
	Sham stimulation bilateral sham transauricular nerve stimulation for the duration of the mechanical thrombectomy procedure (AffeX-CT/001 investigational device). The intervention will be repeated for 1h the morning following the mechanical thrombectomy
Primary outcome measure	The primary outcome is Blood pressure variability [Time Frame: 0-24h after mechanical thrombectomy], as calculated from the coefficient of variation of systolic blood pressure

3. Outcome measures

Primary outcome measure

The primary outcome is Blood pressure variability [Time Frame: 0-24h after mechanical thrombectomy], as reflected by the coefficient of variation of systolic blood pressure.

Secondary outcome measures

- 1. Systolic and diastolic blood pressure variability in the first 24h after mechanical thrombectomy [Time Frame: 0-24h after mechanical thrombectomy]: systolic and diastolic blood pressure mean, standard deviation, and coefficient of variation.
- 2. Heart rate variability [Time Frame: 0-24h after mechanical thrombectomy]: time and frequency domain measures of autonomic cardiac modulation.
- 3. NIH Stroke Scale (NIHSS) [Time Frame: recorded before, at 24h after mechanical thrombectomy]
- 4. Organ dysfunction [Time Frame: First seven days after mechanical thrombectomy.] defined as clinical need for intravenous pharmacological support for blood pressure [pressors or intravenous antihypertensive medication]; arrythmias; myocardial injury [high sensitivity troponin]; hospital-acquired infection.

Exposure variables

The exposure is bilateral active or sham transauricular nerve stimulation for the duration of the mechanical thrombectomy procedure (AffeX-CT/001 investigational device), an intervention that is be repeated for 1h the morning following the mechanical thrombectomy (provided the patient remains in Royal London Hospital).

Sample size and randomisation

Sample size calculation

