 BPV formulae are provided in supplementary data. These measures take into account the distribution and linear trends of BP in an effort to reduce the dependency of BPV on mean BP level.
- 2. Autonomic cardiac modulation in the first 24h after mechanical thrombectomy (Holter monitoring).
- 3. Neurological recovery will be reported by recording serial NIH Stroke Scale (NIHSS) scores, an FDA-approved primary outcome measure for stroke in early phase II trials before and 24h after mechanical thrombectomy.[8]

Exploratory objectives

Biomarkers for risk of infection (whole blood leukocyte transcriptomic changes after incubation at 37°C with sterile saline or 100ng/ml lipopolysaccharide for 4h), infections within 7 days of MT and myocardial injury (high-sensitivity troponin) will also be quantified. Cardiac injury will be assessed by measuring high-sensitivity troponin T on admission and 24h after MT.

Sensitivity analysis

For patients discharged before the repeat stimulation intervention or repatriated to referring centres before the repeat intervention, we will undertake a sensitivity analysis. The primary analysis will be repeated once assuming that all patients in the continue group with missing outcomes did not have BPV >20. The analysis will then be repeated again with the opposite assumptions. This will then give the absolute range of how much the results could change if the data were complete. This will also assess the robustness of our analysis of the primary outcome under the assumption that data is missing-not-at-random (MNAR).

5. Other analyses, data summaries and graphs

Clinical management

Clinical management for the treatment allocation will be summarised but not subjected to statistical testing. Numbers (%) and means (SD) or medians (IQR) will be provided separately for each principal exposure group:

- Thrombectomy technique
- General Anaesthesia/ Sedation
- Endotracheal tube inserted?
- Did the patient have any arrhythmias
- Intraoperative hypotension
- Planned level of care.

Process measures

Summary measures will be presented separately for each treatment allocation. All patients with recorded data will be included in the summary. Formal statistical analysis will not be performed. Patient status at follow up (alive/dead; home/hospital) seven days after MT will be presented as number (%).

Safety analyses

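### The SAP's 7-day infection outcome has no respiratory category, so a patient whose only infection is pneumonia is coded as infection-free

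*SAP*

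**What the plan says.** SAP Appendix 1 has an entry for infection up to 7 days after mechanical thrombectomy. Its opening rule is: "This is defined as one or more of the following infections". Six types follow:

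- "Superficial surgical site infection"
- "Deep surgical site infection"
- "Organ space surgical site infection"
- urinary tract infection
- infection of uncertain source
- bloodstream infection confirmed by the laboratory

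The definition of each type is taken from another trial's protocol, which is not among the documents.

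The coding rule has three branches. The outcome is 1 if "At least one of the components of infection is listed as occurring". It is 0 if every component is recorded as none. It is missing if all components are missing, or if at least one is missing and the rest are none.

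The SAP uses infection in two places. Section 3 includes "hospital-acquired infection" in secondary outcome 4 (organ dysfunction, first seven days). Section 4, under exploratory objectives, says that "infections within 7 days of MT" will be quantified. Appendix 1 holds the only definition of infection in either document.

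On collection, the day-seven list in protocol section 6.6 has two items: "Mortality status and in hospital stay seven days after mechanical thrombectomy" and a safety review. No other list in section 6.6 has an infection item.

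**The concern.** The list does not fit the trial's population. Protocol section 5.1 admits patients with acute ischaemic stroke who need thrombectomy under general anaesthesia and/or sedation, and the SAP's clinical management summary records whether an endotracheal tube was inserted. Half of the infection categories concern a surgical wound, the procedure is catheter-based, and there is nowhere to record a chest infection. The coding rule uses the word postoperative. Together with the surgical-site categories, this suggests that the list was carried over from a surgical trial. That is an inference; the SAP does not say so.

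At stake is whether the infection result means what its name says. The protocol's background states that impaired autonomic control promotes infection and that infection matters for outcome. The SAP's general analysis principles require an effect estimate, a 95% confidence interval and a p-value for each secondary outcome. If respiratory infections are counted as no infection, that comparison covers only part of the infections that occur.

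**Working it through.** The plan states no figure for this outcome, so there is nothing to reproduce. The check applies the stated rule to particular patients and then sizes the effect under an assumed rate.

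**Step 1. Composition of the list (SAP Appendix 1).** Surgical-site types: 3 of 6. Other types: 3 of 6. Respiratory types: 0 of 6.

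**Step 2. The rule applied to a patient with pneumonia.**

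| Record | Branch of the rule | Coded value |
|---|---|---|
| Pneumonia only, all six components none | all none | 0 |
| Pneumonia plus a laboratory-confirmed bloodstream infection | at least one present | 1 |
| Pneumonia entered under uncertain source | at least one present | 1 |
| Pneumonia, one listed component missing, other five none | one missing, rest none | missing |

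Only the first row is a wrong 0. The third row gives the right value only through a loose entry: pneumonia has an identified source, so the result would depend on who completed the form.

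**Step 3. Whether the outside definitions repair this.** The SAP cites the other protocol for how each listed type is defined. That governs the six types and does not add a seventh. The content of that protocol could not be checked.

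**Step 4. Size.** Inputs: 36 patients (protocol section 3.1) and an assumed proportion *r* with pneumonia as their only infection, because the documents give no rate. Expected number coded 0 = 36 × *r*.

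- *r* = 5%: 36 × 0.05 = 1.8
- *r* = 10%: 36 × 0.10 = 3.6
- *r* = 20%: 36 × 0.20 = 7.2
- *r* = 30%: 36 × 0.30 = 10.8

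This is about 2 to 11 patients. With 18 per arm (36 ÷ 2 under 1:1 allocation), the range is 0.9 to 5.4 per arm. The counts assume complete infection records. If the 5 dropouts allowed for in protocol section 13.1 had no infection data, 36 − 5 = 31 remain, and the range becomes 31 × 0.05 = 1.6 to 31 × 0.30 = 9.3.

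**Step 5. Whether another route captures these cases.** Protocol section 11.3 first asks for all adverse events on the CRF, then says that an event assessed as not serious is not recorded there as an adverse event. Protocol section 15.2 limits collection to data that will be used in the analysis. A non-serious pneumonia therefore has no assured place in the dataset. Dummy Tables 4 to 6 have no infection row, and Table 7 names only arrhythmia, skin irritation and other.

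**The case against.** The strongest case is that this is a narrow gap in a minor outcome. Infection is not a protocol endpoint; infection biomarkers appear there only under future research (section 2.2.1). The design rationale in section 1.2 concerns blood pressure lability. SAP section 4 treats infection as exploratory. Serious pneumonia would still be seen: it is not among the expected events named in protocol section 11.4, serious events are reported until last follow-up, and the SAP tabulates adverse events by arm. The SAP also reports other adverse events separately above 5% prevalence, which in 36 patients means at least 2 (36 × 0.05 = 1.8).

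Most of this stands, and it limits the point's weight. It does not remove the gap, because SAP section 3 also lists infection under a secondary outcome, and safety reporting does not change the value that the derivation rule assigns.

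A reader might infer more than the documents support:

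- **That every pneumonia is coded as no infection.** Step 2 shows that some cases are coded 1 or missing.
- **That pneumonia is the leading infection after stroke.** Neither document ranks infection types or gives rates.
- **That the surgical-site categories can never apply.** An arterial puncture site can become infected, and a site might record that as a superficial surgical-site infection.
- **That the outcome can show neither benefit nor harm.** It still counts urinary, bloodstream and source-uncertain infections.

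**Conclusion.** The point holds in this form: under the written rule, a patient whose only infection is pneumonia, with all six components recorded as none, is coded as having no infection. This follows from the text and needs no outside figure. The range of about 2 to 11 of 36 patients rests on the assumed 5% to 30% rate of pneumonia as the only infection and on complete records.

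It affects the exploratory infection objective and the infection part of secondary outcome 4, on the reading that Appendix 1 supplies the definition for both. The primary endpoint, the sample size and the main conclusion are untouched. The plan should be corrected here, but the error does not threaten the trial's central result.

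**What to change.** In SAP Appendix 1:

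- Add pneumonia/lower respiratory tract infection, with a named definition.
- Replace the three surgical-site categories with arterial access-site infection.
- Keep urinary tract, bloodstream and source-uncertain infection, and let the existing 1/0/missing rule run over the revised list.
- If respiratory infection was left out on purpose, say so and rename the outcome to match what it counts.

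In the protocol's day-seven data list and the CRF, add the same tick-list. Section 6.8 already provides for a record review or a call at that point. While editing, state whether infection is secondary or exploratory and give it a row in the dummy tables. Make the change before outcome data are inspected by allocation, in keeping with the SAP's stated remit.

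The cost is a short SAP revision, one added CRF item, and some record retrieval for patients repatriated to other hospitals. Where those records cannot be obtained, the outcome is coded missing, so the number analysed may fall.
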